In order for a wound to heal multiple processes must work in concert. The tissue must receive adequate arterial flow, the bacterial burden must be controlled, the environment must have a proper moisture balance, and negative mechanical forces must be eliminated. Wounds can vary in size and depth; wounds can be clean with a predominance of healthy granulation tissue or have nonviable or necrotic material present, which inhibits healing.

The acute wound which is common, heals in a predictable and orderly fashion. Healing begins with initiation of the clotting cascade, which in turn results in the proteolytic cleavage of fibrinogen by the enzyme thrombin, forming an insoluble blood clot. The blood clot holds damaged tissues together and provides the provisional matrix required for the natural healing process. In addition the outer layer of the clot dries out and creates a degradable crust formed from erythrocytes and other blood components. This tough shell protects the wound from contact with environmental hazards, reduces pain, protects the wound from bacterial contamination, and enables a moist wound environment under it, allowing the repair process to take place unhindered. The clot is a provisional extracellular matrix (ECM), which harbors cytokines and growth factors released by the degranulation of activated platelets and other cells within the clot. The acute wound beneath the clot heals and the remaining dry crust is shed exposing the reconstructed skin.

Chronic wounds such as diabetic ulcers, pressure ulcers and venous ulcers, on the other hand do not heal or heal slowly because an underlying defect (e.g. diabetes mellitus, continued pressure that impedes local blood flow and vascular problems.) arrests progress through the phases of wound healing. Most commonly chronic wounds stall in the inflammatory phase of wound healing characterized by the presence of non-viable tissue, excessive bacterial burden, and the presence of increased inflammatory cytokines.

With aging comes a 20% loss in dermal thickness, making the skin of many elderly adults almost transparent in appearance. The subcutaneous fatty layer also becomes thinner, especially on the face, neck, back of the hands, and shins. If traumatized, these areas will absorb more energy than other parts of the body because they lack cushioning fatty subcutaneous tissue; thus, they are at increased risk for an injury such as a skin tear. The skin has less resilience – sufficient force exerted against the skin will result in a tearing-type injury. Once a skin tear is present in the elderly, the slower rate of epidermal cell turnover prolongs healing time. Alterations in collagen and protein synthesis also may contribute to delayed skin tear healing. In addition, the skin's microcirculation collapses, increasing risk of bruising and reducing blood supply to the skin (the latter can prolong healing time if a break in the skin occurs). Because of the decreased immune response of the geriatric patient, skin tears have a higher risk of becoming infected than in the non-geriatric patient.

The formation of a whole blood clot occurs through a cascade of events. Two pathways lead to the formation of the final blood clot: the intrinsic and extrinsic pathways. Although they are initiated by different distinct mechanisms, the two converge on a common pathway leading to the same fibrin clot formation. The clot formation on an acute wound is through the extrinsic pathway while the in vitro clot formation is through the intrinsic pathway.

A blood clot is the body's natural and optimal provisional wound matrix. As described above, it protects the wound and serves as a provisional matrix into which cells can migrate. The use of the RD1 as a provisional matrix in the management of chronic wounds recreates the natural healing process. Moreover, the function of a blood clot as a provisional matrix has been validated and reported extensively in literature and in 2 clinical studies conducted with the RD1. There are several commercial available matrix or scaffold products. However, all of these products are derived from foreign material: animal tissue or human donor skin. An autologous blood clot matrix should have no immunologic rejection or risks associated with the use of animal products.

The RD1 is created by drawing the patient's blood with the use of citrate anticoagulant. The anticoagulant allows the clot to form later in a controlled fashion—citrate is a widely used anticoagulant. The blood is then placed in the clotting tray (within few minutes) and the coagulation is facilitated by adding calcium and kaolin (insoluble aluminum silicate). The forming clot assumes the shape of the tray containing it, and can then be applied to the wound, and then covered with primary and secondary dressings.

The use of the citrate anticoagulant is essential to the process. Withdrawing blood without the use of an anticoagulant would immediately initiate the coagulation cascade and within minutes a whole blood clot would form. Citrate, which is widely used in the blood banking industry, prevents clotting by binding calcium ions. Clotting can be re-initiated in vitro by adding the calcium ions to the citrated blood. The clotting time can be further accelerated by mixing the blood with a contact surface such as kaolin (insoluble aluminum silicate).

The investigational product, the RD1 kit, was designed to enable a care provider to create an in vitro blood clot from the patient's own blood at the point of care, in a safe and effective manner. The RD1 kit involves currently accepted medical procedures of halting the coagulation process and re-initiating the natural occurring process.

The proposed protocol (RD004) should be sufficient to determine the safety of RD1 in wounds of various etiology, such as Diabetic foot ulcers, pressure ulcer, venous ulcers and skin tears. This takes into account the suppositions that the proposed product is natural in origin (i.e., not synthetic), is not derived from animals but is autologous, and that it attempts to mimic the body's own healing mechanisms of replacing missing Extra Cellular Matrix (ECM) with a fibrin-based matrix, a defect which exists in the local areas of chronic ulcers. Furthermore the RD1 safety was validated in 2 clinical studies of 30 patients with wounds of various etiologies.

1. OVERVIEW

1.1. Study Objectives

Primary Objective

The primary objective of this protocol is:

1. Efficacy- The performance of RD1 in terms of wound progress towards closure in wounds deemed suitable for treatment with RD1

Secondary Objectives:

Secondary objectives of the trial are:

1. Safety - Determine complication rates for all adverse events compromising serious adverse events, adverse events (AEs), and device-related adverse events (DRAEs); AEs include any lack of venous access events
2. Efficacy - Assess the incidence of complete wound closure at 16 weeks for wounds treated with RD1 (defined as skin re-epithelialization without drainage or dressing requirements).
3. Efficacy - Assess the wound Percent Area Reduction (PAR)
4. Efficacy- Assess the optimal duration between applications of RD1 per wound parameter
5. Efficacy- Assess the need of design and procedure improvements of the RD1 for specialized nursing facilities (SNF)
6. Sub Group Analysis – asses the safety and efficacy per wound etiology
7. Asses the cost of RD1 procedure in SNF compared to cost of treatment before RD1
8. Assess wound pain compared to wound pain during treatment before RD1
9. Assess medical staff wound related weekly labor of wound treatment before and during RD1.

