1.4. Study Duration

The study is expected to last 12 to 24 months.

The study per each subject will continue for up to 16 weeks of RD1 treatment (not including up to 2-week screening period (\pm 2 days)), Any wounds that are considered initially healed within the 16-week period will require a confirmatory visit two weeks after healing of before discharge from the SNF (the earlier of the two) to assess durability of wound closure.

Patients will be treated with RD1 every 7 days (\pm 3 days), investigator can prolong the duration between treatments based on medical decision. Total treatment duration is up to 16 weeks or until complete healing.

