If the X-Ray is inconclusive regarding osteomyelitis, further investigation can be undertaken at the discretion of principal investigator. As stated below in the exclusion criteria, patients with underlying osteomyelitis will be excluded.
- 1.6.1.22** During the screening period the wounds will be treated weekly with standard of care treatment .
- 1.6.1.23** Investigator subjective wound pain assessment (appendix XX)
- 1.6.1.24** Medical staff wound related weekly labor assessment for the week prior to initiation of the screening (appendix XX) (optional per sponsor instruction)
- 1.6.1.25** Wound treatment cost assessment for the period prior to initiation of screening (at least weekly cost, preferably monthly cost, if

possible- cost since start of wound treatment)-)optional per sponsor instruction).

1.6.2 Treatment Phase Initial (Day 0):

- 1.6.1.1** Adverse event assessment.
- 1.6.1.2** Ulcer and blood related concomitant medication review.
- 1.6.1.3** Investigator subjective wound pain assessment
- 1.6.2.1** Photography before and after cleansing and debridement (if applicable)
- 1.6.2.2** Wound measurement by photography. Two measurements- before and after cleansing and debridement.
- 1.6.2.3** Wound depth measurement by accepted method. Unit of measurement is millimeters. Two measurements- before and after cleansing and debridement
- 1.6.2.4** Ulcer cleansing
- 1.6.2.5** Ulcer debridement as needed
- 1.6.2.6** Application Regimen: as per the investigators Brochure. Up to 3 RD1 dressings can be applied on each wound on each visit, according to wound size and investigator decision of subject health. The RD1 will be removed or applied only by the research staff.
- 1.6.2.7** Wound related staff labor assessment (optional per sponsor instruction)

1.6.3 Treatment Phase. (Weeks 1-16): The following treatments and assessments are performed during the treatment phase weeks 1-16. During the treatment phase there are 2 types of visits: **1. RD1 Change Assessment Visit** **2. RD1 Change Visit** (performed immediately after Change Assessment Visit).

1.6.3.1 RD1 change assessment visit procedures every 7 days (± 3 days):

- 1.6.3.1.1** RD1 change will be assessed by investigator
- 1.6.3.1.2** Wound/ blood related adverse event assessment
- 1.6.3.1.3** Assess offloading compliance when applicable.
- 1.6.3.1.4** Assess moisture control when applicable.
- 1.6.3.1.5** Ulcer and blood related concomitant medication review.
- 1.6.3.1.6** Photo the RD1 on the ulcer.

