- 1.6.3.1.7** Assessment of the edges of the wound to assess infection.
- 1.6.3.1.8** Assessment of the adherence of the RD1 to the wound.

1.6.3.2 RD1 re-application visit procedures (occurs if investigator decides to change RD1, should occur immediately after RD1 change assessment visit):

- 1.6.3.2.1 Investigator subjective wound pain assessment pre RD1 removal
- 1.6.3.2.2 Removal of old RD1
- 1.6.3.2.3 Photography after RD1 removal, before cleansing and debridement.
- 1.6.3.2.4 Wound measurement by photography. Two measurements- before and after cleansing and debridement.
- 1.6.3.2.5 Wound depth measurement by accepted method. Unit of measurement is millimeters. Two measurements- before and after cleansing and debridement
- 1.6.3.2.6 Wound assessment.
- 1.6.3.2.7 Ulcer cleansing.
- 1.6.3.2.8 Ulcer debridement as needed.
- 1.6.3.2.9 Assess wound infection.
- 1.6.3.2.10 Application Regimen: as per the investigators Brochure. Up to 3 RD1 dressings can be applied on each wound on each visit, according to wound size and investigator decision of subject health. The RD1 will be removed or applied only by the research staff.
- 1.6.3.2.11 Assessment of wound closure
- 1.6.3.2.12 Wound related staff labor (optional per sponsor instruction)
- 1.6.3.2.13 RD1 clot residues sent to analysis

1.6.3.3 Wound healing confirmatory visit. Will be performed to assess durability of wound closure. Performed at the earlier of the 2 options: 1. before discharge from SNF. 2. Two weeks after complete healing. For wounds that have healed during the 16 weeks of active treatment.

- 1.6.3.3.1 Wound size measurement by photography.
- 1.6.3.3.2 Wound depth measurement by accepted method. Unit of measurement is millimeters
- 1.6.3.3.3 Investigator assessment of healing
- 1.6.3.3.4 Physical examination
- 1.6.3.3.5 Adverse event assessment.
- 1.6.3.3.6 Assess offloading compliance.
- 1.6.3.3.7 Concomitant medication review.
- 1.6.3.3.8 Laboratory: complete blood count, PT, PTT, and HbA1c
- 1.6.3.3.9 Offloading (for up to 2 weeks after wound healing, when applicable)
- 1.6.3.3.10 Investigator subjective wound pain assessment
- 1.6.3.3.11 Wound related staff labor during the whole RD1 treatment period (optional per sponsor instruction)
- 1.6.3.3.12 Wound treatment cost during the whole RD1 treatment period

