13.2.2. Secondary Endpoints

- Safety - Determine complication rates for all adverse events compromising serious adverse events, adverse events (AEs), and device-related adverse events (DRAEs); AEs include any lack of venous access events (ITT and Safety Population)
- Efficacy - Assess the incidence of complete wound closure at 16 weeks for wounds treated with RD1 (defined as skin re-epithelialization without drainage or dressing requirements) (ITT population).
- Efficacy - Assess the wound Percent Area Reduction (PAR) (ITT population)
- Efficacy- Assess the optimal duration between applications of RD1 per wound parameter (ITT population)
- Efficacy- Assess the need of design and procedure improvements of the RD1 for specialized nursing facilities (SNF) (ITT population)
- Sub Group Analysis – asses the safety and efficacy per wound etiology (subgroup of ITT population)
- Asses the cost of RD1 procedure in SNF compared to cost of treatment before RD1 (ITT population)
- Assess wound pain compared to wound pain during treatment before RD1 (ITT population)
- Assess medical staff wound related weekly labor of wound treatment before and during RD1. (ITT population)

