5. If there is disagreement between the site assessor and the imaging reviewer, then the Medical Monitor will adjudicate using best judgment, and communicate any change in wound status back to the site assessor. The Medical Monitor will also have access to wound images and data from patient visit records.

APPENDIX 6

TRAINING AND STANDARDIZATION OF CARE AT CENTERS

All study personnel will be trained in the care of ulcers and specific procedures as noted below:

Centers will follow debridement techniques according to appendix 8 of this protocol.

Centers will follow photography techniques according to appendix 3 of this protocol

Centers will follow infection assessments technique according to appendix 11 of this protocol

Centers will follow moisture control assessments technique according to appendix 12 of this protocol

Centers will follow offloading techniques according to appendix 13 of this protocol

Centers will follow wound grading system according to appendix 9 of this protocol

APPENDIX 7
SCHEDULE OF EVENTS

PROCEDURES	SCREENING PHASE (DAY 0)	RD1 CHANGE ASSESSMENT VISIT	RD1 RE-APPLICATION VISIT	HEALING CONFIRMATORY VISIT (if applicable)	END OF STUDY/ EARLY TERMINATION VISIT
Informed Consent	X				
Inclusion/Exclusion	X				
Medical History	X				
Physical Exam	X			X	X
Demographics	X				
Ulcer classification and grading	X				
Neuropathic assessment (Foot Ulcers only)	X				
Infection assessment	X	X	X	X	X
Assessment of moisture control	X	X	X	X	X
Vascular perfusion assessments (when relevant)	X				
Laboratory tests	X			X	X
X-Ray of the study ulcer	X (only if osteomyelitis is suspected)				
Ulcer and blood related concomitant Meds	X	X	X	X	X
Standard of care therapy	X				
Ulcer cleansing and debridement	X		X		X
RD1 change assessment		X			
Apply RD1	X (day 0 only)		X		
Wound photography	X	X	X	X	X
Wound measurement/assessment	X	X	X	X	X
Adverse Event	X	X	X	X	X
Offloading Compliance Assessment	X	X	X	X	X
Pain Assessment	X		X	X	X
Staff labor assessment	X		X	X	X
Pre-RD1 wound treatment cost assessment	X (on screening)				
RD1 procedure cost assessment	X (on day 0)			X	X

APPENDIX 8

DEBRIDEMENT

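### Secondary objective 4 presents an 'optimal' interval between RD1 applications as efficacy, although no alternative intervals are assigned or compared

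*Protocol*

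**What the plan says.** Protocol 1.1 lists nine secondary objectives. The fourth, labelled efficacy, is to "Assess the optimal duration between applications of RD1 per wound parameter". Section 13.2.2 repeats it as an endpoint for the ITT population, which 13.1.2 defines as subjects who complete the study.

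Section 1.2 describes a single-arm study. Sections 1.4 and 1.5 set treatment every 7 days (±3) for all subjects, for up to 16 weeks, and add that the "investigator can prolong the duration between treatments based on medical decision". Neither section states criteria for prolonging or an upper limit.

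Section 1.6.3.1 says how the decision is made. At the assessment visit, "RD1 change will be assessed by investigator". The same visit includes a photograph of the RD1 on the ulcer, a check of the wound edges for infection, and "Assessment of the adherence of the RD1 to the wound". The re-application visit in 1.6.3.2 "occurs if investigator decides to change RD1, should occur immediately after RD1 change assessment visit".

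**The concern.** An optimum implies that some intervals were compared with others and one did best. Here the only planned interval is the nominal one, and departures from it follow what the investigator sees. If longer and shorter intervals are then compared on healing, the comparison mixes any effect of the interval with the reasons for choosing it. If wounds doing well tend to be left longer, long intervals look good even when the interval has no effect; if wounds doing badly are left longer, they look poor.

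At stake is one efficacy-labelled statement about how often RD1 should be changed, which later users could take as evidence for an interval when it may only describe which wounds were left alone.

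**Working it through.** The protocol gives no figure for this objective, so there is none to reproduce. The check sets the sections side by side, with some schedule arithmetic.

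1. **Are alternative intervals allocated?** No. Section 1.2 has one arm, and 1.4 and 1.5 give one schedule. No section allocates subjects, wounds or periods to different intervals.

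2. **Which intervals can arise?** Sixteen weeks is 16 × 7 = 112 days. Starting on day 0, a 7-day interval gives 112 / 7 = 16 applications, which equals the maximum in 1.2. A 14-day interval gives 112 / 14 = 8. A 4-day interval, the short end of the window, would need 112 / 4 = 28, above that maximum. Over a full course the average interval can therefore hardly fall below 7 days, and sustained variation comes mostly from lengthening.

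3. **Why would an interval lengthen?**
   - By choice: the investigator leaves the RD1 on after the inspection in 1.6.3.1, or prolongs under 1.4.
   - By missed visits: section 6 withdraws a subject only after more than two consecutive misses. Two misses that are not made up early give 3 × 7 = 21 days, nominally, with no decision about the RD1.
   - By interruption: 4.1.1 allows treatment to stop for topical antimicrobials, which may not be combined with RD1, and resume later. Section 7.4 requires removal before referral because of an adverse event and allows resumption in some cases. In both, the gap includes days with no RD1 on the wound.

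   Time between applications is therefore not the same quantity as time in place.

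4. **What could 'optimal' mean?**
   - Judged by healing: the interval follows the investigator's view of the RD1 and the wound, so confounding by indication applies. Its direction depends on which wounds are left longer, and the protocol does not say.
   - Judged by how long an RD1 stays serviceable: the photographs and adherence checks fit, but the result is a description of wear, not an efficacy optimum.

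5. **Which periods does the analysis set contain?** Section 13.1.2 keeps completers only, and section 9 likewise limits the secondary objectives to them. Wear periods that ended in withdrawal are lost under either reading. Section 13.1.1 already defines a set of all subjects with at least one RD1 treatment.

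6. **Is the wound measured when RD1 is left on?** None of the 8 items in 1.6.3.1 is area or depth. Of the 13 items in 1.6.3.2, two are, both after removal: depth, and "Wound measurement by photography. Two measurements- before and after cleansing and debridement". Yet Appendix 7 marks "Wound measurement/assessment" at the assessment visit. Appendix 2 requires RD1 to cover the whole wound and at least 0.5 cm of surrounding skin, so area is not expected to be visible then. The row can be read as assessment alone, but the two places should agree.

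**The case against.** The strongest reply is that the protocol nowhere says healing will be compared across intervals. Section 13.2 sends the analysis to the SAP, and the data collected suit a wear-time reading: photographs of the RD1 in place, adherence, and clot residues sent for analysis (1.6.3.2.13). Nor does the efficacy label prove a healing comparison, since objective 5, on design and procedure improvements, carries it too. This stands. The healing comparison is only one reading, and a reader who infers that it is planned goes beyond the text. The reply does not rescue the wording, because on the wear-time reading 'optimal' and the label are still wrong. Nor can an SAP supply allocated intervals; it could only adjust for recorded factors, under strong untestable assumptions.

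A reader might also infer that no interval is assigned at all. Sections 1.4 and 1.5 contradict that: a nominal interval applies to all subjects, and what is missing is an alternative to compare it with.

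A third inference would be that the missing measurements at assessment visits make adjustment impossible. The documents do not support this. An ordinary wear period is bracketed by measurements at the application that starts it and the re-application that ends it, and area hidden under the RD1 is hidden from the investigator too. What remains is the mismatch between 1.6.3.1 and Appendix 7.

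Finally, many gaps can be traced: 12.1 requires source documents to explain missed or out-of-window visits, and section 7 records action taken and outcome for adverse events. This lowers the cost of the fix but does not make the gaps part of an RD1's wear.

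**Conclusion.** The point holds as a minor one. Objective 4 promises an optimum that a single arm with investigator-prolonged intervals cannot establish as an efficacy result. That follows from the design and the wording, whatever the SAP contains. The conclusion on confounding depends on 'optimal' being judged by healing. The conclusions on the label, on the completer-only set and on gaps without RD1 hold under both readings.

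No size can be given. The protocol states neither how often intervals will be prolonged, nor in which wounds, nor a drop-out rate. A reader should not infer a bias of known amount or direction, or a known loss of subjects. One of nine secondary objectives is affected; the primary endpoint, complete closure, percent area reduction and safety are not.

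**What to change.** In 1.1 and 13.2.2:

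- Replace 'optimal' and the efficacy label with a descriptive objective: the time each RD1 stayed in place and its adherence, by wound characteristic, in all treated subjects (13.1.1).
- Report time between applications separately, since it can include time with no RD1 on the wound.
- Treat removal at the scheduled week-16 visit (1.6.3.4) as administrative censoring, and tabulate removals for early termination or referral by reason.
- State that any comparison of healing across investigator-chosen intervals is exploratory and will not be used to infer an optimal interval.

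Separately, reconcile 1.6.3.1 with Appendix 7 on whether area and depth are measured when RD1 is left in place.

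The cost is the wording of one objective and one endpoint, a change of analysis set, and one reconciled schedule row. Photographs and adherence are already listed. The reason for removal is listed in neither 1.6.3 nor Appendix 7, so one case report form field may be needed. The sponsor gives up the claim to an optimal interval. No change to the treatment schedule is proposed.
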